4. OBJECTIVES*

In this study, we will develop Vaper-to-Vaper (V2V), a suite of mobile peer driven tools, including peer texting and coaching, based on lessons learned in our prior tobacco intervention work. These tools will engage and help adolescents use strategies to manage cravings and successfully quit e-cigarettes. The specific aims of the V2V study are to:

Aim 1: Adapt the existing peer-driven and gamification mobile tools to develop the V2V intervention.

1A. Conduct a qualitative study to (1) explore issues unique to e-cigarette use (e.g., concerns, motivations, triggers, symptoms of nicotine dependence), and (2) understand perceived needs for cessation support (preferences for technology (e.g., texting, app-based) to inform adaptation of the toolset.

1B. Work with these users to build the V2V innovations, including peer messaging for adolescents, peer-to-peer videos, and game narratives for gamification.

1C. Refine the V2V mobile toolset with iterative usability testing (mini-pilot).

There are no hypotheses for Aim 1. Aim 1 is just to adapt the existing peer-driven and gamification mobile tools to develop the V2V intervention.

Aim 2: Evaluate the feasibility of the research protocols and the feasibility and acceptability of the V2V intervention (peer messaging, peer coaching, and gamification) compared to e-cigarette cessation written materials (control) in a pilot feasibility study.

2A. Assess the feasibility of the research protocols, including participant recruitment and retention.

***Hypothesis H1:** We will be able to recruit 80 adolescents (20/school, 40 per study condition), and $\geq 85\%$ will be retained in each study condition at 6-month follow-up.*

2B. Monitor V2V engagement (e.g., number of responses to texting quizzes, peer coaching interactions, peer videos viewed) and assess acceptability of and satisfaction with the program.

2C. Assess preliminary effect size estimates of the V2V intervention on cotinine-validated 7-day point prevalence abstinence, time to first quit attempt, and amount of use.

***Hypothesis H2:** The intervention will be associated with greater cotinine-validated 7-day point prevalence vaping abstinence rates, lower time to first quit attempt, and less amount of e-cigarette use compared to control at 6-month follow-up.*

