Inclusion criteria for key informants: (1) employed as a school nurse, Vice Principal, or other academic administrator at a participating high school.

Exclusion criteria for key informants: (1) unable or unwilling to participate in the study.

Vulnerable Populations

Pregnant Women

Pregnant women may be included in this study as an incidental population.

Adults Unable to Consent

Adults unable to consent will not be included in the study population.

Prisoners

Prisoners will not knowingly be included in the study population.

Children

We will be recruiting adolescents in grades 9 through 12, aged 13-19 years old. The rationale for targeting adolescents in this study is that the FDA and the US Surgeon General call the increasing use of e-cigarettes among U.S. adolescents an epidemic, with e-cigarette use exceeding combustible cigarette use. The high amounts of nicotine in e-cigarettes harm adolescent brain development, impacting learning, memory, and attention. Adolescent e-cigarette users also are at higher risk than non-users of transitioning to traditional cigarettes. We are therefore interested in applying lessons learned in developing interventions for adolescents and another challenging population, low motivated adult smokers. Study investigators have extensive experience with conducting research with adolescents and a reputation for designing culturally sensitive, patient-centered programs, and we are accountable to those standards. Please see Section #11, *Procedures Involved*, and Section #30, *Consent Process*, for more information.

We will include English- and Spanish-speaking individuals in this study. Should the intervention be proven efficacious, we will apply for further funding and plan to include additional non-English speaking populations in future studies.

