how it worked/did not work; **iii)** their thoughts regarding our initial concepts; and **iv)** what they feel would help students use a mobile program. Interviews will employ a semi-structured open-ended approach, allowing for natural conversation with opportunities to explore unanticipated issues. Interviews will be recorded, transcribed, and coded.

The semi-structured interview is expected to last no more than 60 minutes. We will provide a \$100 gift card to the key informants for completion of this interview.

Compensation: Gift cards totaling up to \$120 (\$20-\$30 for each activity and the mini pilot) will be provided to adolescents for completion of Aim 1 activities. Gift cards of \$100 will also be provided to the key informants (school nurse and Vice Principal) and to the school nurses assisting with study activities (e.g., serving as the on-site point person for study recruitment, referring students requesting additional information regarding the study to research staff). There are two nurses at the high school, and we will provide a \$100 gift card per nurse.

See also Section #30, *Consent Process*.

Aim 2

We will recruit from 4-7 local high schools (that were not involved in Aim 1), selected for their high rates of racial/ethnic minorities and low SES status. Prior to recruitment, the study team will obtain IRB approval for the specific schools. To reduce the chances of imbalance across conditions, the schools will be matched based on percentage low income, percentage African American, and number of students, and divided into two sets of two. Within each set of two, we will randomly assign one school to each of the study conditions.

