Aim 2A (Feasibility) Hypothesis H1: *We will be able to recruit 80 adolescents (20/school, 40 per study condition), and $\geq 85\%$ will be retained in each study condition at 6-month follow-up.* We will estimate recruitment rates, overall and per condition. Also, for each condition, we will model 6-month retention, using generalized estimating equation (GEE) logistic regression to account for within-school clustering and dependence over time.

Proposed Sample Size. As appropriate for a pilot study, we are estimating our power and sample size based on the feasibility hypothesis (H1). Because pilot studies do not provide meaningful estimates of effect sizes due to the imprecision inherent in small samples, we base our proposed sample size of 40 students per condition (20 per school) on obtaining precision in estimating condition-specific retention rates, providing important information for design and recruitment for the future R01 study. Based on our prior study of adolescent smoking cessation, estimated intra-school correlation=0.01, for a design effect due to within-school clustering of $1 + [0.01 \times (20 - 1)] = 1.19$, and an effective sample size per condition of $40/1.19 = 34$. Based on our prior studies in

adolescents in school settings, we anticipate at least 85% retention. Thus, a conservatively wide 95% exact CI for per-condition retention rate is (68.9%, 95.0%).

Aim 2B (Monitor V2V Engagement and Assess Program Satisfaction) As the trial progresses, we will monitor engagement overall and by participant subgroups (e.g. by gender, race, age) as a formative assessment. Then, as the trial ends, we will also use this information as a component of our summative evaluation. We anticipate that engagement will lead to positive changes in acceptability, and satisfaction, and cessation.

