Aim 2C (Cessation Outcomes) *Hypothesis H2: The intervention will be associated with greater cotinine-validated 7-day point prevalence vaping abstinence rates, lower time to first quit attempt, and less amount of e-cigarette use compared to control at 6-month follow-up.* We recognize that there is some controversy about estimating effect sizes from pilot studies. However, we are calculating effect sizes in our study to provide a range, recognizing that there might be uncertainties because of our small sample size. To estimate effect sizes for V2V intervention versus control, between-condition differences over time will be estimated for **cotinine-validated 7-day point prevalence abstinence** using GEE logistic regression with a random effect for school and fixed effects of condition, time point (baseline and 6 months), and their interaction. Missing data is handled using inverse probability weighting. By taking the repeated measurements into consideration, the GEE model is able to increase the power to test the difference in the outcome. COX regression modeling will be used to examine the intervention effect on **time to first quit attempt** adjusting for other covariates. **Amount of e-cigarette use** will be calculated as a reduction from baseline. We will model this reduction using negative binomial regression modeling if the variance of the distribution of risk reduction is over dispersed.

Other information important for the design of a future study includes standard deviations, as well as **preliminary assessment of possible mediators** such as engagement, behavioral capability, and self-efficacy. We will identify important mediators in exploratory analyses. Guided by the conceptual model based on SCT, we will assess effects of intervention on the mediator and the

effects of the mediator on the outcome, controlling for other mediators in the model, and confounders of the mediator-outcome relationship, and then estimate the proportion of the intervention effect explained. Given the limited sample size, conclusions from the mediation analyses will be limited and treated with caution, but modeling will allow us to explore the constructs of SCT and potential predictors towards a larger RCT.

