25. LOCAL NUMBER OF SUBJECTS

The local number of subjects for this study is as follows:

Aim 1: 20 adolescent e-cigarette users (peer advisory panel) and 2 key informants (school nurse and vice principal) from 1 high school.

Aim 2: 80 adolescent e-cigarette users from four high schools selected for their high rates of racial/ethnic minorities and low SES status (20/school, 40/study condition) will be recruited and complete assessments at baseline and 6-month follow-up. With a conservative 85% retention rate, we will achieve a total of 68 e-cigarette users (17/school, 34/study condition) at 6-month follow-up. We will also recruit up to 12key informants (school nurses, vice principal, or other academic administrator) from participating high schools.

Overall, we plan to recruit up to 110 individuals.

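### The H2 abstinence contrast claims power to test and has no small-cluster method, although only four schools, in two matched pairs, are randomised

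*Combined protocol and SAP*

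**What the plan says.** **Hypothesis.** Section 4 and Section 13 (Aim 2C) word H2 with a direction: "The intervention will be associated with greater cotinine-validated 7-day point prevalence vaping abstinence rates", with matching statements for time to first quit attempt and amount of use.

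**Model.** Section 13 (Aim 2C) analyses abstinence by GEE logistic regression with a random effect for school and terms for condition, time point and their interaction. It credits the repeated measurements: "the GEE model is able to increase the power to test the difference in the outcome". It gives no alpha, sidedness, decision rule or small-cluster correction for H2.

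**Design.** Section 11 (Aim 2) matches the schools and has them "divided into two sets of two". It continues: "Within each set of two, we will randomly assign one school to each of the study conditions". All students in a school get the same condition. Section 25 has "80 adolescent e-cigarette users from four high schools selected for their high rates of racial/ethnic minorities and low SES status", while Sections 6 and 11 allow four to seven schools.

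**Stated purpose.** Section 10 makes feasibility the primary outcome and lists preliminary effect sizes as secondary. The sample-size paragraph in Section 13 rests on H1 alone, because "pilot studies do not provide meaningful estimates of effect sizes due to the imprecision inherent in small samples". Aim 2C says that effect sizes are calculated to give a range.

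**The concern.** The plan describes H2 as estimation but also speaks of testing it and of gaining power to do so. The unit of randomisation is the school, so the information on between-school variation comes from four units. A method that treats four schools as a large sample gives p-values that are too small and intervals that are too narrow.

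The interval matters most. Aim 2C promises a range of effect sizes, and Section 13 says that the pilot is meant to guide a future R01. If that range looks less than half as wide as it should, the next trial could be planned around an effect that this pilot has hardly constrained.

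**Working it through.** **1. The plan's own figures (H1 only).** Design effect = 1 + 0.01 × 19 = 1.19. Effective n = 40 / 1.19 = 33.6, rounded to 34. The exact 95% interval for 29/34 is 68.9% to 95.0%. All three reproduce. The plan gives no corresponding figure for H2.

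**2. Randomisation floor.** With k pairs there are 2^k equally likely allocations. The smallest p is 1/2^k one-sided and 2/2^k two-sided.

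| Schools | Allocations | One-sided | Two-sided |
|---|---|---|---|
| 4 in 2 pairs | 4 | 0.25 | 0.50 |
| 6 in 3 pairs | 8 | 0.125 | 0.25 |
| 4, matching ignored | 6 | 0.167 | 0.333 |

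**3. Error rate of a school-clustered robust z.** Inputs from the plan are 17 completers per school and two schools per arm (Section 25), and ICC 0.01 (Section 13). Abstinence of 15-30% and the ICC range 0 to 0.05 are assumptions.

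With two equal schools per arm, the uncorrected sandwich variance of an arm's rate is Σ(r_j − r̄)²/2², while the unbiased estimate is Σ(r_j − r̄)²/(2 × 1). The sandwich is half the unbiased value, and it is then referred to 1.96 instead of 4.30.

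Beta-binomial simulation of the 6-month contrast, 200,000 trials per scenario, independence working correlation, nominal 5% two-sided:

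| Method | Rejections under the null |
|---|---|
| Logit contrast, school-clustered robust z | 24-29% |
| School-level t, 2 df | 4.8-5.3% |
| Student-level logit z, ICC 0.01 | about 4-7% |
| Student-level logit z, ICC 0.05 | about 8-14% |

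At ICC 0.01 the school-level t-test has power of about 10% for 10% v 20%, 13.5% for 15% v 30%, and 17% for 20% v 40%.

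**4. Interval width.** Take assumed abstinence of 10% v 20%, 34 per arm, and design effect 1 + 0.01 × 16 = 1.16.

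SE = √[(0.10 × 0.90 + 0.20 × 0.80) × 1.16 / 34] = √0.00853 = 0.0924.

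| Reference | Multiplier | 95% half-width |
|---|---|---|
| z | 1.96 | 18.1 points |
| t, 2 df (unmatched) | 4.30 | 39.7 points |
| t, 1 df (matched pairs) | 12.71 | 117 points |

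The same SE is used throughout, so the contrast is due to the reference distribution alone. The ratio of z to 2 df is 1.96 / 4.30 = 0.46.

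**5. The repeated-measures claim.** Table 2 marks cotinine-validated abstinence at 6 months only. Sections 13 and 26 mention saliva collection at baseline as well. If the outcome exists only at 6 months, it has no repeated measurement from which power could be gained.

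**The case against.** **The plan already calls this preliminary.** Sections 4, 10 and 13 say so, power rests on H1, and no alpha or decision rule exists for H2. The power sentence is a comparative remark about using two time points, not a claim of adequate power. This stands, and it means that rewording H2 alone gains little. It does not repair the interval, which is what a preliminary estimate delivers.

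**The 24-29% is not shown for the planned model.** This also stands. A GEE with a random effect for school combines two kinds of model, and the plan states neither the clustering level nor the variance estimator. A student-level z-test at the plan's ICC of 0.01 rejects only about 4-7% of null trials. A reader might take 24-29% as the error rate of this trial, but it belongs to one common reading of an undefined analysis.

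**A reader might infer that no test whatever can go below 0.5.** The design does not imply that. The 0.50 floor is for the two-sided exact randomisation test with four schools, and the floor in H2's direction is 0.25. Model-based tests can go lower. A paired t-test on assumed pair differences of 0.20 and 0.18 has mean 0.19 and SE 0.01, so t = 19 on 1 df and p = 0.033. Such tests are valid only under distributional assumptions and have very low power.

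**A reader might infer a funding rule** from Section 6: "Should the intervention be proven efficacious, we will apply for further funding". That sentence goes on to future inclusion of further language groups. It explains language coverage and sets no criterion for judging this pilot.

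**Conclusion.** The concern holds as a fault in the analysis specification. Aim 2C claims a gain in power to test, with no small-cluster method, for a comparison that rests on four schools. The randomisation floors (0.50 and 0.25 with four schools, 0.25 and 0.125 with six) follow from the design alone. The inflated rejection rate is conditional on a school-clustered robust z and the assumed abstinence and ICC ranges. The narrowing of the interval to less than half its width on 2 df holds wherever a school-level standard error is paired with z; the 18 and 40 points also assume 10% v 20% abstinence.

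H2 is secondary and described as preliminary, so neither the feasibility objective nor its sample-size argument is affected. The exposure is in the range of effects handed to the next trial.

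**What to change.** - In Section 13 (Aim 2C), delete the sentence on power to test the difference.
- In Sections 4 and 13, align H2 with the stated aim of preliminary estimation, and say that no efficacy conclusion will be drawn.
- Report the abstinence rate in each school, and the between-condition difference with an interval on school-level degrees of freedom. With four schools this is 2 df if the matching is ignored and 1 df if the pairs are kept. State the choice in advance. On the figures above, the 1 df interval exceeds the possible range of a difference in proportions.
- Leave the Section 6 sentence as it is.

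The cost is wording and an interval method, with no change to conduct or sample size. The drawback is that reported intervals become much wider and H2 carries no p-values.

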5. BACKGROUND*

Adolescent e-cigarette use has now exceeded combustible cigarette use, leading the FDA and the U.S. Surgeon General to call the increasing use of e-cigarettes among U.S. adolescents an epidemic.¹⁻⁴ The 2018 National Youth Tobacco Survey found a 78% increase in e-cigarette use in just one year,⁵ with over 3.5 million youth currently using e-cigarettes. Alarmingly, 28% of high school e-cigarette users are vaping on 20 or more days in the past month.⁵ The high amounts of nicotine in e-cigarettes harm adolescent brain development, impacting learning,

memory, attention, mood, and impulse control.⁶ Further, adolescent e-cigarette users are at higher risk than non-users of transitioning to traditional cigarettes.^{1,2,6-10} Tobacco use continues to be the leading cause of preventable morbidity and mortality in the U.S., with nearly all tobacco use beginning during youth and young adulthood.^{11,12} Once transitioned, 80% of these adolescent smokers will continue to smoke into adulthood and, of those, one-half will die 13 years earlier than nonsmoking peers.^{13,14}

Evidence-based and accessible e-cigarette cessation interventions are critically needed to help adolescent e-cigarette users quit.^{1,2,7} To our knowledge, there are currently no evidence-based interventions to assist adolescent e-cigarette users in quitting.^{1,2,7} E-cigarette users are a complex group, including all race and ethnic groups as well as youth of higher and lower socioeconomic status (SES).¹⁵ Although recent concerns regarding vaping and proposed regulatory changes (increasing purchasing age, banning flavors) may increase adolescent interest in quitting and demand for e-cigarette cessation interventions, the perception of lower risk of e-cigarettes may lead to a lower intention to quit,^{16,17} with the majority of youth e-cigarette users believing vaping only includes flavoring and not nicotine.¹⁸ Therefore, novel approaches specifically tailored to their unique needs that can be disseminated broadly are required to engage, educate, motivate, and support adolescent e-cigarette users to successfully quit.

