6. INCLUSION AND EXCLUSION CRITERIA*

Aim 1 Study Population (20 adolescent e-cigarette users (Peer Advisory Panel) and two key informants)

The study population will be derived from 20 adolescent e-cigarette users in one high school selected for its high rate of racial/ethnic minorities and low SES status. We will also recruit two key informants (school nurse and Vice Principal) from the same high school.

Inclusion criteria for peer advisory panel: (1) enrolled in grade 9-12 at a local high school; (2) current e-cigarette user; (3) have a smartphone; and (4) English- or Spanish-speaking. Current e-cigarette user is defined as a response greater than “0 days” to the question: “During the past 90 days, on how many days did you use e-cigarettes?” This eligibility criterion is modeled on a question in the 2018 National Youth Tobacco Survey (NYTS), a survey of U.S. middle and high school students which used a 30-day timeframe.

Exclusion criteria for peer advisory panel: (1) unable or unwilling to provide informed assent or consent (in the case of those aged 18 years or older).

Inclusion criteria for two key informants: (1) employed as a school nurse or Vice Principal at the Aim 1 high school.

Exclusion criteria for two key informants: (1) unable or unwilling to participate in the study.

Aim 2 (80 adolescent e-cigarette users and up to 12 key informants)

In Year 2 of the project, 80 adolescent e-cigarette users in 4-7 high schools selected for their high rates of racial/ethnic minorities and low SES status (20/school, 40/study condition) will be recruited and complete assessments at baseline and 6-month follow-up.

Inclusion criteria for 80 adolescent e-cigarette users: (1) enrolled in grade 9-12 at a participating high school; (2) current e-cigarette user; (3) have a smartphone; and (4) English- or Spanish-speaking. Current e-cigarette use is defined as a response greater than “0 days” to the question: “During the past 90 days, on how many days did you use e-cigarettes?” This eligibility criterion is modeled on a question in the 2018 National Youth Tobacco Survey (NYTS), a survey of U.S. middle and high school students which used a 30-day timeframe.

Exclusion criteria for 80 adolescent e-cigarette users: (1) unable or unwilling to provide informed assent or consent (in the case of those aged 18 years or older).

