With participant permission, we will collect complete and accurate contact information from the student at baseline, including home address, phone, cell phone, email, and phone numbers of three contacts and best times and days to reach them to maximize retention. A contact sheet will be completed by the participant that will include the above information. Care will be taken to maintain the confidentiality of the student's participation; therefore all students will be asked to provide us with the individuals or contact information where they feel comfortable being contacted by study staff or where they feel assured that the confidentiality of their participation will be maintained. The other contacts provided by the student will not be informed of the student's vaping status. We have found in prior studies that cell phone numbers and e-mail addresses are particularly helpful in remaining in contact with this population. Tracking procedures will be implemented for any student who does not attend a scheduled study visit or who is not accessible by telephone or e-mail at the contact location provided. Attempts to locate students will be made mainly through the schools and by telephone calls to the contacts provided or directory assistance.

Table 2. Study Assessments, Measures and Data Collection Timing

Variable and Measure	Relevant Aim	Baseline	6-month follow-up
Recruitment: # screened and eligible, # and reasons for refusal	2A	•	
Retention: # of dropouts, reasons for dropping out	2A		•
Engagement (V2V only): # of completed responses to texting quizzes, peer videos viewed, peer coaching interactions	2B		*
Acceptability and satisfaction: Client Satisfaction Questionnaire (CSQ-8) semi-structured interview	2B		•
Cotinine-validated 7-day point prevalence abstinence: saliva samples collected from all; analyzed for those reporting 7-day abstinence; cut-off 11.4 ng/ml	2C		•
E-cigarette use frequency (past 7 and 30 day) and intensity (# days and amount vaped in past 7 and 30 day)	2C	•	•
THC/marijuana and other tobacco use frequency (past 7 and 30 day) and intensity (# days and amount vaped)		•	•
Social Cognitive Theory (SCT) constructs			
Self-efficacy, confidence to quit: Self-efficacy Questionnaire (SEQ-12)		•	•
Demographics and tobacco use			
Demographics: age, gender, socio-economic status, race/ethnicity, grade in school, academic performance		•	•
History of all tobacco use, past and recent quit attempts, cessation strategies used		•	

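### Amount of use is defined as a reduction from baseline, but the only model named for it, negative binomial regression if over-dispersed, cannot be fitted once any participant vapes more at 6 months

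*Combined protocol and SAP*

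**What the plan says.** In section 13, Aim 2C (Cessation Outcomes), amount of e-cigarette use "will be calculated as a reduction from baseline". The next sentence gives the analysis: "We will model this reduction using negative binomial regression modeling if the variance of the distribution of risk reduction is over dispersed". No model is named for this outcome if that condition is not met.

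Three other places bear on the point:

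- **Hypothesis H2** (section 4, repeated in section 13) concerns the level of use at follow-up, not a change: "less amount of e-cigarette use compared to control at 6-month follow-up".
- **Table 2** (section 11) lists several candidate measures at baseline and 6 months: "E-cigarette use frequency (past 7 and 30 day) and intensity (# days and amount vaped in past 7 and 30 day". Aim 2C does not say which measure or window is the amount.
- **Eligibility** (section 6) needs any answer above zero days to "During the past 90 days, on how many days did you use e-cigarettes". That window is longer than the 7- and 30-day windows in which use is measured.

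Section 10 lists the effect size for amount of use among the secondary outcomes. Section 25 expects 68 participants at 6 months, 17 per school and 34 per condition.

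**The concern.** A reduction is a signed quantity: positive for participants who cut down, zero for no change, negative for those who vape more. Negative binomial regression is a model for the counts 0, 1, 2 and so on. The outcome as defined and the model as named therefore fit together only if nobody increases use.

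The design does not prevent increases. Someone who vaped 60 days ago but not in the last 30 is eligible, has a 30-day baseline of zero, and can then show only a zero or negative reduction.

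The over-dispersion condition has the same weakness, because comparing variance with mean is a diagnostic for counts and loses that meaning once values can be negative. The term *risk reduction* is undefined for an outcome that is an amount.

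At stake is the third of the three outcomes in H2. If the planned model fails, the analyst must choose a remedy with the data in view, and remedies such as setting increases to zero or dropping those participants can change the between-condition estimate.

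**Working it through.** The plan states no figure for this outcome, so there is none to reproduce. The check has four parts.

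**1. Support of the model.** The negative binomial probability at −1 or −3 is 0, so the log-likelihood is minus infinity as soon as one reduction is negative. As an illustration, baseline and 6-month days were simulated for 68 participants, 22 of them with a negative reduction:

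| Outcome and model | Result |
|---|---|
| Reduction, negative binomial by maximum likelihood | log-likelihood −∞, not converged |
| Reduction, negative binomial GLM | stopped with an error |
| Reduction, Poisson | log-likelihood −∞ |
| 6-month value, negative binomial, with or without log baseline | converged, finite likelihood |
| Reduction, linear regression | fitted |

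Poisson, the usual count model without over-dispersion, does not rescue the unnamed branch.

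**2. Any rule for increases.** Sections 10, 11 and 13 contain no floor, shift, exclusion or alternative model for this outcome. The other models in section 13 serve other analyses: GEE logistic regression for retention and abstinence, Cox regression for time to first quit attempt, and linear mixed modelling for engagement against satisfaction.

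**3. Chance that the problem arises.** The share *p* who increase use is not in the documents. The background figure that "28% of high school e-cigarette users are vaping on 20 or more days in the past month" says nothing about change between visits, so *p* is an assumption and is varied.

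- Independent participants: P(at least one increase) = 1 − (1 − *p*)^68. For example, at *p* = 0.01, 1 − 0.99^68 = 0.495.
- Clustered: beta-binomial with four schools of 17 and the intra-school correlation of 0.01 that section 13 uses for the sample size. Applying it to this outcome is a further assumption.

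| Assumed share *p* | Independent | Clustered, ICC 0.01 |
|---|---|---|
| 0.5% | 0.289 | 0.271 |
| 1% | 0.495 | 0.469 |
| 2% | 0.747 | 0.720 |
| 5% | 0.969 | 0.960 |
| 10% | 0.999 | 0.999 |

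At an assumed ICC of 0.05, the 5% row becomes 0.920. Under independence, a share of about 1% gives an even chance and 4.3% gives a 95% chance.

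**4. What an unplanned workaround could do.** These two cases are hypothetical and in days. The difference is mean reduction in V2V minus mean reduction in control.

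- *Case A.* In control, 40% increase by 6 days and 60% reduce by 3. In V2V, 40% do not change and 60% reduce by 3. Control mean: 0.4(−6) + 0.6(3) = −0.6. V2V mean: 0.6(3) = 1.8. True difference: 2.4. Increases set to zero: 1.8 − 1.8 = 0. Increasers dropped: 1.8 − 3.0 = −1.2.
- *Case B.* In both conditions 40% increase by 6 days; the other 60% reduce by 3 in control and by 7 in V2V. Control mean: −0.6. V2V mean: 0.4(−6) + 0.6(7) = 1.8. True difference: 2.4. Set to zero: 4.2 − 1.8 = 2.4. Dropped: 7 − 3 = 4.0.

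With 5% in place of 40%, case A has a true difference of 0.3 against 0 and −0.15, and case B 3.8 against 3.8 and 4.0.

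**The case against.** The strongest reply has three parts.

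**Wording.** The negative binomial is conditional, and the authors may have meant a count model of use at both visits, with the reduction read from the condition-by-time term; *risk reduction* is ratio language. The condition is real: what is shown is that the one named branch fails with any negative value and that the other branch is empty for this outcome. The two-visit reading is weaker, because the text first calculates a reduction and then says that this quantity is what will be modelled. Under that reading too, the text would need correcting.

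**Evidence of bias.** Cases A and B rest on invented shares and sizes, and evaluate workarounds that the plan does not propose. That stands. They show only that the choice of workaround can matter and that its direction is not predictable; at a 5% share the distortions are 0.2 to 0.45 days. It is also fair that the over-dispersion check would be meaningful if the measure is a count and nobody increases use.

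**Weight.** This is one secondary estimate in a pilot sized on retention, and section 13 itself warns that effect sizes from small samples are imprecise. The failure would probably be visible, since software would stop or not converge, so a silent wrong answer is unlikely. This limits the harm to a model chosen after the fact. It does not remove it: a caution about imprecision does not cover an estimate that cannot be computed as specified.

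**Conclusion.** The concern holds and should be fixed. The outcome as defined can be negative, the model named for it cannot take negative values, and nothing in the documents bridges the two. This rests on reading reduction as baseline minus follow-up; with the sign reversed, everyone who cuts down would be negative and the same failure would follow.

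How likely the failure is depends on an unknown share, but an assumed share of only 1% to 5% gives a 50% to 97% chance of at least one negative value among 68 independent completers, and 47% to 96% with the clustering used for the sample size. The size of any resulting bias cannot be stated from the documents.

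The reach is limited to the preliminary effect size for amount of use. Recruitment, retention, sample size, abstinence and time to first quit attempt are unaffected.

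**What to change.** In section 13, Aim 2C, name one Table 2 measure and one window as the amount of use, then specify one of the following:

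- **(a)** Model the 6-month value with condition and baseline use as covariates. This matches H2. Use a count model suited to the measure, check its fit because days out of 7 or 30 are bounded, and enter baseline on a scale that allows zero.
- **(b)** Keep the change score and analyse it by linear regression adjusted for baseline.

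Under either option, keep participants who increased use, and delete the over-dispersion condition on the change score and the term *risk reduction*.

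Two details can be settled in the same edit, though the finding does not depend on them. First, state how school, the assigned unit, is accounted for. With schools "divided into two sets of two", about two per condition, cluster-adjusted standard errors are fragile, so the interval is best presented as descriptive. Second, the sentence "Missing data is handled using inverse probability weighting" follows the abstinence model; say whether it also covers this outcome.

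The cost is wording only, since Table 2 already collects the measures at both visits. The choice must be made before the data are seen. A count model under (a) reports a ratio rather than a change in days and may fit bounded days poorly, in which case (b) is simpler.
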